13.1.5. Relationship

It is the investigator's responsibility to assess the relationship between the IMP and the AE. The degree of "relatedness" of the AE to the IMP may be described using the following scale:

- Not Related: No temporal association and other etiologies are likely the cause
- Unlikely: While cannot be definitively ruled as not related to IMP, a causal association is remote, and other etiologies are more likely to be the cause. For reporting and summarization, events assessed as Unlikely to be related to IMP will be considered as Not Related to IMP.
- Possible: Temporal association, but other etiologies are likely the cause. However, involvement of the IMP cannot be excluded.
- Probable: Temporal association, other etiologies are possible but unlikely. The event may respond if the IMP is discontinued.
- Definite: Established temporal association with administration of the IMP with no other more probable cause. Typically, the event should resolve when the IMP is discontinued and recur on re-challenge.

13.1.6. Monitoring and Follow-up of Adverse Events

Patients having AEs will be monitored with relevant clinical assessments and laboratory tests, as determined by the investigator. All follow-up results are to be reported to the Sponsor personnel or the authorized Medical Monitor. Any actions taken and follow-up results must be recorded either on the appropriate page of the eCRF or in appropriate follow-up written correspondence, as well as in the patient's source documentation. Follow-up laboratory results should be filed with the patient's source documentation.

For all AEs that require the patient to be discontinued from the study, relevant clinical assessments and laboratory tests must be repeated at appropriate intervals until final resolution or stabilization of the event(s).

Patients with AEs related to IMP that are ongoing at study discontinuation or completion must be followed until resolution or for 30 days after study completion, whichever comes first, with the exception of patients reporting SAEs (see Section 13.2.4).

13.1.7. Treatment-Emergent Adverse Events

TEAE are defined as AEs that begin or worsen after randomization and the first dose of double-blind IMP.

13.2. Serious Adverse Events

13.2.1. Definition of Serious Adverse Event

An SAE is defined as any AE occurring at any dose that results in any of the following outcomes:

- Results in death
- Is life-threatening
- Requires in-patient hospitalization or prolongation of existing hospitalization
- Results in persistent or significant disability/incapacity, or substantial disruption of the ability to conduct normal life functions
- Is a congenital anomaly/birth defect
- An important medical event

NOTE: An emergency room visit without hospital admission will not be recorded as an SAE under this criterion, nor will hospitalization for an elective or outpatient procedure scheduled or planned before signing of informed consent. However, unexpected complications and/or prolongation of hospitalization that occur during elective or outpatient surgery should be recorded as AEs and assessed for seriousness. Admission to the hospital for social or situational reasons (eg, no place to stay, live too far away to come for hospital visits) will not be considered inpatient hospitalizations.

Important medical events that may not result in death, be life threatening, or require hospitalization may be considered an SAE when, based upon appropriate medical judgment, they may jeopardize the patient and may require medical or surgical intervention to prevent one of the outcomes listed in this definition. Examples of such medical events include allergic bronchospasm requiring intensive treatment in an emergency room, blood dyscrasias, convulsions that do not result in inpatient hospitalization, or the development of drug dependency or drug abuse.

13.2.2. Events or Outcomes Not Qualifying as Serious Adverse Events

The following are not considered SAEs and therefore do not need to be reported as such:

- Preplanned or elective hospitalization including social and/or convenience situations (eg, due to inclement weather)
- Overdose of either Esperion study drug or concomitant medication unless the event meets SAE criteria (eg, hospitalization). However, the event should still be captured as a nonserious AE on the appropriate eCRF page.

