13.2.4. Reporting Serious Adverse Events

All SAEs occurring from the time of informed consent until 30 days following completion or discontinuation of study must be reported by the Principal Investigator or designee to the designated Safety contact within 24 hours of the Principal Investigator or the clinical site becoming aware of the occurrence. All SAEs that the investigator considers related to IMP that occur after the 30-day follow-up period of the study period must be reported to the Sponsor. As a reminder, adjudicated clinical endpoints will NOT be reported as SAEs in the eCRF and will NOT be reported in an expedited manner as an SAE since these events are known to occur in this patient population.

To report the SAE, the SAE information should be entered into the EDC RAVE database within 24 hours of becoming aware of the occurrence. Additional documentation, such as laboratory or diagnostic test results or discharge summaries may be sent separately via email

 If you have questions, please call the designated Safety contact for assistance. All contact information is provided on the SAE report form for this study.

Detailed instructions and contact information for the Global and Regional Safety and Medical Monitor(s) will be provided in the SAE Completion Guidelines.

The investigator is required to submit SAE reports to the IRB/IEC in accordance with local requirements. All investigators involved in studies using the same investigational product will receive any safety alert notifications for onward submission to their local IRB as required. All reports sent to investigators will be blinded.

All SAEs should be recorded on the eCRF and source documents. Criteria for documenting the relationship to IMP and severity will be the same as those previously described.

The investigator must continue to follow the patient until the SAE has subsided or until the condition becomes chronic in nature, stabilizes (in the case of persistent impairment), or the patient dies.

Within 24 hours of receipt of follow-up information, the investigator must update the SAE form and submit any supporting documentation (eg, patient discharge summary or autopsy reports) to the designated Safety contact.

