15.8.1. Adverse Events of Special Interest (AESI)

All AESI will be identified and evaluated by routine safety monitoring of AEs and laboratory values (where appropriate) and will be summarized by severity and relationship to IMP for each treatment group.

The following are considered AESI categories for this study:

- Hepatic Safety, including liver-associated enzymes, TB, and any Hy's law cases ($\geq 3 \times$ ULN for either ALT or AST, with accompanying TB $>2 \times$ ULN in the setting of no known other cause)
- Musculoskeletal Safety, including CK
- Diabetes and Glycemia, including new onset of diabetes and worsening of diabetes
- Hypoglycemia Associated with Metabolic Acidosis
- Renal Impairment, including lab measures of renal function
- Neurocognitive Events
- Atrial Fibrillation
- Tendon Rupture/Tendinopathy. The TRAC will adjudicate events of tendon rupture per the TRIAC, and adjudicated events will be summarized.
- Malignancies

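### Protocol 13.2.1 and 13.2.2 classify an elective inpatient admission arranged after consent in opposite ways, so its SAE status is undefined

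*Protocol*

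**What the plan says.** Protocol 13.2.1 lists the outcomes that make an AE serious. One is: "Requires in-patient hospitalization or prolongation of existing hospitalization". The criterion does not separate emergency from planned admissions. A note under the list takes some hospital contacts out of this criterion. For elective care the exemption is tied to a date: "nor will hospitalization for an elective or outpatient procedure scheduled or planned before signing of informed consent". The same note keeps complications in scope: "unexpected complications and/or prolongation of hospitalization that occur during elective or outpatient surgery should be recorded as AEs and assessed for seriousness". It also takes out admissions for social or situational reasons.

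Protocol 13.2.2 opens with: "The following are not considered SAEs and therefore do not need to be reported as such". Its first bullet is: "Preplanned or elective hospitalization including social and/or convenience situations". The bullet mentions neither consent nor when the underlying condition began. The second bullet, on overdose, does carry an override for events that meet the SAE criteria and gives hospitalization as its example. The first bullet has no such override.

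Protocol 13.2.4 sets the reporting window: "All SAEs occurring from the time of informed consent until 30 days following completion or discontinuation of study must be reported". Admissions arranged during follow-up therefore fall inside it.

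**The concern.** Patients are followed for years, and some of the conditions that appear in that time will be dealt with by a scheduled admission. Such an admission can be planned well after consent. A site working from 13.2.1 would then report an SAE. A site working from 13.2.2 would enter a non-serious AE. With about 1,200 sites in 32 countries, both readings are likely to be applied.

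Several things depend on the flag:

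- the 24-hour report to the Safety contact, and onward reporting to ethics committees and regulators (Protocol 13.2.4);
- follow-up: related AEs still open at study end are followed to resolution or for 30 days, whichever is sooner, but SAEs are excepted from that limit (13.1.6) and are followed until they subside, stabilize, become chronic or the patient dies (13.2.4);
- the duty to report related SAEs that occur after the 30-day period (13.2.4);
- the serious TEAE tables (SAP 16.1.1) and the exposure-adjusted incidence rates for SAEs (SAP 16.1.4).

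**Working it through.** No formula applies, because the point turns on wording. The check applies both sections to each type of admission, then looks for text elsewhere that settles or limits the conflict.

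**Case by case**

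| Admission | 13.2.1 | 13.2.2 | Result |
|---|---|---|---|
| Elective procedure planned before consent | Exempt | Exempt | Consistent |
| Social or situational admission | Exempt | Exempt | Consistent |
| Complication or prolonged stay during elective surgery | AE, assessed for seriousness | Silent | No contradiction |
| Elective inpatient admission arranged after consent for a new or worsened condition | Meets the hospitalization criterion and falls outside the exemption: SAE | Excluded: not an SAE | **Contradiction** |
| Coronary revascularization adjudicated as an endpoint | Not reported as an SAE (13.2.5) | Not reported as an SAE (13.2.5) | Unaffected |

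The conflict is confined to the fourth row. It arises because 13.2.2 joins preplanned and elective with *or*, so being elective is enough by itself, and because the bullet carries no date limit.

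**Does other text decide which section governs?** None of the supplied text does. Protocol 13.2.4 refers sites to SAE Completion Guidelines, which are not among the documents. The AESI descriptions in 13.3 are blacked out.

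**What limits the consequence**

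- Protocol 13.1.3 has the condition that led to a procedure recorded as an AE, so the event stays in the database.
- SAP 16.1.2 identifies AESIs by preferred term or laboratory criterion. Seriousness plays no part.
- For tendon rupture, Protocol 15.8.1 adds: "The TRAC will adjudicate events of tendon rupture per the TRIAC, and adjudicated events will be summarized".
- The other criteria in 13.2.1, including important medical event, can still make the event serious. The exposed group is therefore events whose only ground for seriousness is the elective admission.
- The primary endpoint comes from adjudicated events. The sponsor's search for missed endpoints covers both AE and SAE reports (Protocol 11.1), so it does not depend on the flag.

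**Size.** The share of such events coded non-serious would be the product of three quantities: the share of admissions that are elective, the share of sites that follow 13.2.2, and the share of events with no other ground for seriousness. The documents give none of them. Suppose, purely as an assumption, that 30 to 60% of admissions are elective and that no event has another ground for seriousness. Letting the share of sites run from 0 to 1 then gives 0.30 × 0 = 0 up to 0.60 × 1 = 0.60. A range of 0 to 60% is no guide, so no estimate is offered.

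**The case against.** The best defence is that the 13.2.2 bullet covers the same ground as the note in 13.2.1 (planned or elective care, plus social admissions) and is meant as a short restatement of it. A site trained on that note may apply the consent limit without noticing a difference, and the SAE Completion Guidelines may say so outright. This is possible and cannot be excluded. The protocol text does not say it, however, and the override on the neighbouring overdose bullet makes the unqualified elective bullet look deliberate. Guidance elsewhere would reduce the practical effect but would not remove the contradiction from the protocol.

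The defence is right to resist two stronger readings.

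- A reader might infer that tendon, cancer or arrhythmia events treated by planned surgery drop out of the safety data. They do not. Each remains an AE and belongs to an AESI category that is captured without regard to seriousness, and tendon rupture is adjudicated as well. The documents do not say how often such care is elective.
- A reader might also infer that the trial loses ability to detect a safety difference between arms. SAP 16 plans no statistical comparison of safety data unless otherwise specified. The overall TEAE and AESI rates in SAP 16.1.4 do not use the serious flag, so only the SAE rates could be under-counted.

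**Conclusion.** The contradiction is real but narrow. An elective inpatient admission arranged after consent, for a condition that arose or worsened on study, is an SAE under Protocol 13.2.1 and not under 13.2.2. Where it is the only ground for seriousness, classification, expedited reporting, follow-up duration and the serious-event tables depend on which section the site used.

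The likely effect is some under-counting and inconsistent classification of SAEs, of unknown size. Sites are blinded and the same text applies to both arms, so the documents give no reason to expect a distortion between arms. The primary efficacy analysis is not touched. The conclusion assumes that no unsupplied or blacked-out text resolves the conflict; it does not rest on any assumed rate. The point is worth correcting because an operative reporting rule gives two answers and the remedy is small.

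**What to change.** Reconcile the first bullet of Protocol 13.2.2 with 13.2.1. Limit it to (i) hospitalization for a procedure already scheduled or planned when consent was signed and (ii) admission for social or convenience reasons, and add a cross-reference to the note in 13.2.1. This adds no condition that 13.2.1 does not already contain.

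SAP 15.2.3 dates the start of closeout to 15 May 2022. If an amendment would come too late to guide sites, a memo to sites can carry the same clarification.

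In either case, before unblinding, query AEs entered as non-serious that have a linked inpatient admission and have the investigator reassess seriousness under 13.2.1. The AE items listed in Protocol 13.1.3 do not include a separate hospital-admission field, so the query may have to draw on procedure records or source documents.

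The cost is one line of protocol text or a memo, slightly more SAE reports, and one round of data queries.

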13.2.3. Clinical Laboratory Assessments as Adverse Events and Serious Adverse Events

It is the responsibility of the investigator to assess the clinical significance of all abnormal values as defined by the list of reference ranges from the corresponding laboratory. In some cases, significant changes in lab values within the normal range will require similar judgment.

An abnormal laboratory value that is not already associated with an AE is to be recorded as an AE only if any one of the following criteria is met:

- an action on the study drug is made as a result of the abnormality
- intervention for management of the abnormality is required
- at the discretion of the investigator should the abnormality be deemed clinically significant

13.2.4. Reporting Serious Adverse Events

All SAEs occurring from the time of informed consent until 30 days following completion or discontinuation of study must be reported by the Principal Investigator or designee to the designated Safety contact within 24 hours of the Principal Investigator or the clinical site becoming aware of the occurrence. All SAEs that the investigator considers related to IMP that occur after the 30-day follow-up period of the study period must be reported to the Sponsor. As a reminder, adjudicated clinical endpoints will NOT be reported as SAEs in the eCRF and will NOT be reported in an expedited manner as an SAE since these events are known to occur in this patient population.

To report the SAE, the SAE information should be entered into the EDC RAVE database within 24 hours of becoming aware of the occurrence. Additional documentation, such as laboratory or diagnostic test results or discharge summaries may be sent separately via email

 If you have questions, please call the designated Safety contact for assistance. All contact information is provided on the SAE report form for this study.

Detailed instructions and contact information for the Global and Regional Safety and Medical Monitor(s) will be provided in the SAE Completion Guidelines.

The investigator is required to submit SAE reports to the IRB/IEC in accordance with local requirements. All investigators involved in studies using the same investigational product will receive any safety alert notifications for onward submission to their local IRB as required. All reports sent to investigators will be blinded.

All SAEs should be recorded on the eCRF and source documents. Criteria for documenting the relationship to IMP and severity will be the same as those previously described.

The investigator must continue to follow the patient until the SAE has subsided or until the condition becomes chronic in nature, stabilizes (in the case of persistent impairment), or the patient dies.

Within 24 hours of receipt of follow-up information, the investigator must update the SAE form and submit any supporting documentation (eg, patient discharge summary or autopsy reports) to the designated Safety contact.

The Sponsor (and/or legally transferred designee) will report SAEs and suspected and unexpected serious adverse reactions (SUSARs) as required by global regulatory authorities, IECs/IRBs, investigators/institutions in compliance with all reporting requirements according to local regulations, laws, and GCPs. The investigator should notify the appropriate IEC/IRB of SAEs occurring at the site and other AE reports received from the Sponsor, in accordance with local procedures and statutes.

13.2.5. Events Exempt from (Serious) Adverse Event Reporting

Adjudicated clinical endpoints will NOT be reported as AEs or SAEs and will NOT be reported in an expedited manner as an SAE to the designated Safety contact since these events are known to occur in this patient population.

All SAEs that occur during the course of the study, whether or not causally related to the IMP, must be reported immediately (within 24 hours of the investigator becoming aware of the event), except for clinical endpoints defined as the following:

- CV Death
- Non-CV Death
- Nonfatal MI
- Nonfatal stroke
- Hospitalization for unstable angina
- Coronary revascularization

A clinical endpoint that is reported by the site but, upon subsequent review by the CEC, is adjudicated to NOT meet all of the clinical endpoint criteria as defined by the CEC Charter will be reclassified as an AE, SAE, or procedure as appropriate. If that reclassified event meets one or more of the seriousness criteria for AEs, the event must be reported in an expedited manner (within 24 hours of notification of investigator) as an SAE to the designated Safety contact in the same manner as other SAEs. In this instance, the date of awareness of the event for SAE reporting purposes will be the day that the investigator is informed that the reported clinical endpoint did not meet clinical endpoint criteria adjudicated by the CEC. At the time that a clinical endpoint is reported, information will also be collected that would be required if, in the future, it is determined to be an SAE. This information will include AE term, severity, action taken with IMP, relatedness, etc.

13.2.6. Reporting of Patient Death

The death of any patient during the study or within 30 days after study discontinuation or completion must be treated as a clinical endpoint for adjudication. This event will not be reported as an SAE.

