11. ASSESSMENT OF EFFICACY

11.1. Reporting of Clinical Endpoints

All clinical endpoints occurring at any point from signing the ICD until 30 days after completion of the study will be reported by the site and adjudicated by the CEC according to guidelines detailed in the CEC Charter. Study sites will complete the relevant clinical endpoint eCRFs and obtain other required source documents in a timely fashion as per study-specific instructions contained in the Endpoint Manual.

Clinical endpoints include any of the following:

- CV Death (MACE)
- Non-CV Death (non-MACE clinical endpoint)
- Nonfatal MI (MACE)
- Nonfatal stroke (MACE)
- Hospitalization for unstable angina (non-MACE clinical endpoint)
- Coronary revascularization (MACE)

Detailed definitions of these clinical endpoints are included in the CEC Charter and the Endpoint Manual. Please note that the Sponsor will also review blinded AE and SAE reports on a routine basis in order to identify potential additional clinical endpoints. AEs and SAEs that are identified by the Sponsor as potential clinical endpoints will be reviewed by the CEC and may result in a request to the site that additional source documentation be obtained or adjustments to reporting in the eCRF be completed.

An adjudicated clinical endpoint will not be reported as an AE nor, if appropriate, as an SAE in the eCRF. Additionally, it will NOT be reported in an expedited manner as an SAE since these events are expected to occur in this patient population.

A clinical endpoint that is reported by the site but, upon subsequent review by the CEC is adjudicated to NOT meet all of the clinical endpoint criteria as defined by the CEC Charter, will be reclassified as an AE, SAE, or procedure as appropriate. If that reclassified event meets one or more of the seriousness criteria for AEs, the event must be reported (within 24 hours of notification of investigator) as an SAE in the same manner as other SAEs. In this instance, Day 1 for SAE reporting purposes will be the day that the investigator is informed that the reported clinical endpoint did not meet clinical endpoint criteria adjudicated by the CEC. At the time that a clinical endpoint is reported, information will also be collected that would be required if, in the future, it is determined to be an SAE. This information will include AE term, severity, action taken with IMP, relatedness, etc.

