Any clinical endpoint occurring after the 30-day follow-up period that the investigator becomes aware of and considers related to IMP must be reported to the Sponsor as an SAE.

Please contact your monitor regarding any questions about the reporting of clinical endpoints and whether these clinical endpoints should be reported as AEs and/or SAEs.

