16.1.2. Adverse Events of Special Interest

 AESIs will be identified by specified MedDRA PTs, or the related laboratory criteria if applicable. See [Appendix 7](#) for the list of AESIs and their definitions. These events will be summarized by AESI category, laboratory criteria met (if applicable), and PTs.

The NODM AESI is applicable only for patients with baseline glycemic status ([Section 7.4](#)) of No Diabetes at baseline. As an AESI vs. an efficacy endpoint, NODM includes a broader definition of NODM with patients who meet one of the following conditions:

- patients with verified NODM as determined by the DC ([Section 7.4.3](#)), or
- patients who initiated a diabetes medication after first dose of IMP ([Appendix 8](#)), or
- patients meeting the laboratory criteria for NODM as in [Appendix 7](#), or
- patients with selected AE preferred terms (see list of preferred terms for ‘NODM’ in [Appendix 7](#)).

Worsening Hyperglycemia AESI is applicable to patients with baseline glycemic status of Diabetes based on adverse event preferred terms as described in [Appendix 7](#).

See [Appendix 7](#) for the list of AESIs and their definitions. AESIs will be identified by specified MedDRA PTs, and/or the related laboratory criteria if applicable. These events will be summarized by treatment group, and by AESI category, laboratory criteria met, and PTs.

Malignancy AESI will be summarized by Standardised MedDRA Queries (SMQs) and PTs as described in [Appendix 7](#).

Tendon rupture will be summarized for events that are positively adjudicated according to the TRAC Charter. All potential tendon ruptures that were reviewed by the TRAC will be presented in a listing.

For AEs considered to be muscle related by the Investigator, additional information is collected on the *Muscle Related Adverse Event Complementary* CRF including the primary cause, locations, and whether the AE is unilateral or bilateral.

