16.2. Death and Major Adverse Cardiac Events

For this study deaths and positively adjudicated MACE (MI, stroke, coronary revascularization, hospitalization for unstable angina) are study endpoints and per protocol are not recorded in the Adverse Event CRF. They will be reported as adjudicated endpoints in listing and tables using the FAS.

In addition, all events leading to death as reported by the Investigator will be summarized by SOC/PT and treatment group using the SAS, and for patients in the SAS with baseline ezetimibe use.

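### A non-CV death the investigator considers drug-related has no SAE route until 30 days after the study, and a fatal event with no earlier AE entry is left out of the SAP's main serious-event summaries

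*Protocol*

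**What the plan says.** Protocol 13.2.5 starts from a broad rule: "All SAEs that occur during the course of the study, whether or not causally related to the IMP, must be reported immediately". It then makes an exception, "except for clinical endpoints defined as the following", and the list that follows includes both CV and non-CV death. Section 11.1 also names non-CV death as an endpoint: "Non-CV Death (non-MACE clinical endpoint"). The reason given in 13.2.5 is that such events belong to the background of these patients: adjudicated endpoints "will NOT be reported in an expedited manner as an SAE to the designated Safety contact since these events are known to occur".

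Section 13.2.6 covers every death during the study or within 30 days of leaving or completing it. Such a death "must be treated as a clinical endpoint for adjudication. This event will not be reported as an SAE". The SAE definition in 13.2.1 still has death as its first criterion.

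Causality reopens the SAE route in one place only, the end of 11.1: "Any clinical endpoint occurring after the 30-day follow-up period that the investigator becomes aware of and considers related to IMP must be reported". The report then goes to the sponsor, in the form of an SAE.

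On the analysis side, SAP 16.2 says that deaths and positively adjudicated MACE "are study endpoints and per protocol are not recorded in the Adverse Event CRF". They are reported as adjudicated endpoints in the FAS. The same section adds a table, by SOC, PT and arm in the safety set, of investigator-reported events leading to death. SAP 16.1.2 says "AESIs will be identified by specified MedDRA PTs", or by laboratory criteria where these apply.

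**The concern.** Exempting endpoints from SAE reporting is reasonable when the events are the disease under study. That argument fits MI, stroke, revascularization and CV death. Non-CV death is a residual category. It would include fatal liver failure, renal failure and cancer, and the protocol names hepatic safety, renal impairment and malignancy as AESI categories (15.8.1). Section 4.2.2 gives the liver (rats, monkeys) and kidney (monkeys) as target organs in toxicology. Nothing in the documents explains why such deaths should be presumed to be background.

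Two things are at stake. The first is prompt individual reporting of a fatal suspected reaction. The second is completeness of the serious-event counts by arm: the most severe form of a named risk may be counted in a different table from its non-fatal forms.

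**Working it through.** The plan states no figure on this point, so the check is a reading of the rules side by side.

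**Step 1. One case at three times.** Take a non-CV death that the investigator considers related to study drug.

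| Time of death | Governing text | SAE report by the site? |
|---|---|---|
| On treatment | Protocol 13.2.5, 13.2.6 | No |
| Day 29 after study completion | Protocol 13.2.6 | No |
| After the 30-day follow-up | Protocol 11.1, final rule | Yes |

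**Step 2. Can reclassification return it?** Sections 11.1 and 13.2.5 turn an endpoint back into an AE or SAE when the CEC finds that endpoint criteria are not met. CV death and non-CV death are both endpoints, so a death moved out of one class falls into the other. The trigger is endpoint status, not relatedness.

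**Step 3. Does a related answer trigger anything?** Relatedness, AE term and severity are collected when an endpoint is reported, for use if the event is later found to be an SAE. By step 2 a death would not normally reach that point. No other step is stated.

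**Step 4. Follow the case through the SAP.** Suppose the illness had no AE entry before death.

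- Serious and treatment-related TEAE tables (16.1.1) are built from AEs: not counted.
- Exposure-adjusted rates (16.1.4) use the same events: not in the numerator. The patient's time still enters the denominator up to the date of last assessment, which 7.2.1 sets to the date of death if death came within 90 days of the last visit.
- AESI counts (16.1.2): counted only if a laboratory criterion is met.
- Events leading to death (16.2): counted, by SOC, PT and arm.
- Adjudicated deaths in the FAS: counted as a non-CV death.

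If the illness had been entered as an AE before death, as Protocol 13.1.3 requires of AEs in general, the first three would count it.

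**Step 5. Size.** Planned follow-up is 14,000 × 3.5 years = 49,000 patient-years. The documents give no non-CV death rate. Assuming 0.25 to 1.5 per 100 patient-years:

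- 49,000 × 0.0025 = 122.5
- 49,000 × 0.015 = 735

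That range is how many non-CV deaths might fall under the exemption, both arms together. It is a ceiling. The deaths that matter are the subset judged related (for reporting) and the subset with no earlier AE entry (for the tables), and neither can be estimated from the documents.

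**The case against.** The case for leaving the plan alone has substance, and it rules out several stronger readings.

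- A reader might infer that SUSAR reporting is waived for these deaths. It is not. Protocol 13.2.4 keeps the sponsor's commitment to report SUSARs under all applicable rules, and relatedness is collected with the endpoint. What is missing is the step that connects the two.
- A reader might infer that nobody sees these deaths by arm during the trial. The DMC reviews unblinded data, including clinical endpoints, about 4 times a year (Protocol 14.2). That is periodic review and does not replace prompt reporting of a single case, but it is real oversight.
- A reader might infer that all fatal events vanish from the safety tables. The texts exempt the death, not the illness before it. A cancer or hospitalized hepatic event reported at onset is already an AE or SAE. Hepatic cases may also be picked up from laboratory values (SAP 16.1.2, 16.3), and fatal terms have their own table.
- A reader might call the 30-day rule a contradiction. The rules are sequential: the CEC channel runs to 30 days after the study, and the SAE channel takes over for related events. The asymmetry is a gap.
- A reader might want non-CV death removed from the exempt list altogether. That is a trade-off, because all-cause mortality is a key secondary endpoint and the deaths must still go through adjudication. The narrower change does not need it.

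What remains is that the site's 24-hour route is closed for a related fatal event on drug with no stated substitute, and that fatal events without a prior AE entry sit outside the serious, related and exposure-adjusted summaries.

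**Conclusion.** The gap is real but narrow. Followed exactly, the protocol gives the site no SAE route for a non-CV death it considers related, from consent until 30 days after the study, and no text carries the related answer to the Safety contact. The SAP consequence is confined to fatal events with no earlier AE entry: absent from the serious TEAE, treatment-related and exposure-adjusted summaries, absent from AESI counts unless a laboratory criterion is met, and present in the table of events leading to death.

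This reading assumes that the SAP's AE tables draw on the AE form and that no unseen document fills the gap. The AESI detail in Protocol 13.3 is redacted, and SAP Appendix 7, the CEC Charter, the Endpoint Manual and the SAE Completion Guidelines are not in the public text. The documents also do not say whether the illness behind a death stays on the AE form. The number of deaths affected is unknown. The efficacy analyses are untouched. This is a worthwhile, inexpensive improvement, not a flaw that undermines the trial.

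**What to change.** 1. **Protocol.** Reconcile 11.1, 13.2.1, 13.2.4, 13.2.5 and 13.2.6 by applying the related-endpoint rule at the end of 11.1 to non-CV deaths during the study and the 30-day window as well. Keep sending these deaths to the CEC.
2. **SAP 16.1.1, 16.1.2 and 16.1.4.** Add the investigator-reported fatal terms for treatment-emergent non-CV deaths to the serious TEAE, treatment-related, exposure-adjusted and AESI counts, once per patient and term. Alternatively, give the same counts as a supplementary summary beside the planned tables.

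The cost is a few more SAE reports and slightly higher SAE and AESI counts. No new data are needed: AE term, severity and relatedness are collected with each endpoint, and SAP 16.2 already plans to tabulate the fatal terms by SOC and PT. Part 1 needs an amendment with IRB or IEC approval (Protocol 20.3) across about 1200 sites in 32 countries. SAP 15.2.3 dates the start of closeout to May 15, 2022, so part 1 can do little for this trial. Part 2 can still change what is reported.
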